In order to lay the groundwork for a future Merit Review proposal investigating the utility of spatial cognitive training in visual rehabilitation, the currently proposed SPiRE project seeks to establish the feasibility of such training in visually impaired participants over a telehealth interface, to obtain data on the effect size of the training relative to a control intervention to provide a basis for sample size estimation in a larger clinical trial, and to examine the relevant neural mechanisms so as to suggest possible synergistic interventions that would enhance the effects of spatial cognitive training. Importantly, the proposed work will examine the real-world generalizability of the training effects using physical walking spaces to assure relevance to rehabilitation.

Research Design and Methods

PARTICIPANTS

We will recruit 60 blind participants, randomized by our CVNR statistician into two groups. One group will undergo the experimental intervention (spatial cognitive training) and the other will undergo a control intervention involving letter-number matching. The participants will include women and minorities in proportion to the demographics of the veteran population attending the Atlanta VA. Working with our statistician, we calculated that this sample size has a power of 0.81 to detect an effect size of 0.9 with $\alpha=0.05$ and $\beta=0.19$. The randomization process should result in a balance between the intervention and control groups with respect to a range of variables, including age, sex, age of onset of visual loss, duration of visual loss and of loss of light perception, and comorbid conditions; any residual differences will be accounted for as covariates in statistical analyses.

Since the participants are blind or have low vision, they will need transportation to the CVNR, which will be provided via a contractual arrangement in place with the CVNR. Subjects will be compensated for their time at a flat rate of \$150 for participation in all sessions of the study. If they drop out or are otherwise unable to complete the study, compensation will be prorated for the number of sessions they participate in.

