Study flow (Fig. 2): Participants will take part in an initial session of behavioral testing and fMRI scanning, and another similar session after training. In the intervening 3 weeks, they will attend 12 training sessions of one hour each, comprising either the experimental or control intervention. These sessions will take place each weekday from Monday-Thursday, beginning the Monday after the initial session, and will be conducted via the internet with the participant at home, using CVNR-issued iPads. The Friday of each week will be used for repeat testing on the spatial imagery task to assess the extent of improvement as a result of the preceding four days' training. This design allows 12 hours of training over 3 weeks, comparable to that used in prior studies of spatial cognitive training (Wright et al., 2008; Terlecki et al., 2008). In addition, it allows us to

assess weekly improvement, thus providing crucial data for design of a larger study in the future. Importantly, CVNR investigators have experience using iPads with their built-in accessibility for those with visual impairments, and experience with this kind of telehealth application. They have found that even older, technologically naïve caregivers (mean age 78±4.1) can learn to use novel technologies such as the iPad; with a high degree of reported satisfaction (Griffiths et al., 2016). Specifically, Co-investigator [name] has expertise in use of telehealth technology with visually impaired participants in a VA project where he assessed the accessibility of smart phones including the iPhone and in an NIH SBIR project in which the accessible and award-winning MoneyReader app was developed for the iPhone and iPad. The training sessions will employ a haptic grid overlay on the iPad screen during training, and

software will be developed to enable remote communications and viewing of the subject's movements and finger position on the screen of the iPad.

Spatial imagery task: The imagined grid used for the spatial imagery task as well as for spatial cognitive training will be a 5x5 grid using the numbers 1-25, with 1-5 on the first row from left to right, 6-10 on the second row from left to right, and so on (**Fig. 3**). Participants will first

Initial positions: white numbers. Arrows: shortest paths from initial to final position, intersecting with mentally traced sequence (right) or not (left).

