Interventions: The experimental intervention (spatial cognitive training) will comprise repeated practice of the spatial imagery task with feedback after each trial. Training will be conducted in the participant's home using an iPad issued to the subject at the initial visit, and live video communication with a research assistant at the CVNR over the internet. The iPad will be programmed to allow administration of the spatial imagery task. As in the version of the spatial imagery task administered at initial and final testing, audio cues will trigger mental navigation through the grid using audio cues, with haptic reinforcement via tactile overlays for the screen (to permit sensory facilitation of learning). Following each sequence traced, subjects will be asked whether the shortest path back to the origin intersects with the sequence traced or not. If the answer is incorrect, the research assistant will show the correct path for the subject to trace mentally and haptically. In the control intervention, subjects will be taught letter correspondences to the numbers (e.g. 1->A, 2->B and so on until 25->Y), using a similar setup and procedure as in the experimental intervention.

Behavioral measures: The following behavioral measures will be collected before and again after training with the experimental and control interventions: (1) Performance (directional accuracy and response time [RT]) on the spatial imagery task will be acquired during fMRI scanning. (2) In addition, pointing accuracy will be measured on the real-world path integration task in the MSL, in terms of the angular difference between the target of pointing and the actual initial position. (3) We will also measure performance, with standardized neuropsychological tests, at baseline as well as at post-training, on (a) spatial memory using a haptic version (produced in the [name] lab using textured blocks) of the Corsi block test (Kessels et al., 2000), (b) the verbal memory tests of immediate and delayed memory from the RBANS (Randolph, 1998) and (c) verbal working memory tested by the Forward and Backwards Verbal Digit Span test from the Wechsler Adult Intelligence Scale (Wechsler, 2008). A research assistant will be trained by the PI and [name], Co-investigator on this project, to administer all the tests, as well as the training procedures.

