Specific Aim I will test the hypothesis that spatial cognitive training of blind veterans on a spatial imagery task leads to improvements in **(a)** performance on the trained spatial imagery task and **(b)** real-world navigational ability, relative to a control intervention. If the hypothesis is supported, this would be a simple method of spatial cognitive training with real-world benefits that could eventually be administered via telemedicine. **Specific Aim II** will use functional magnetic resonance imaging (fMRI) to assess the neural changes associated with spatial cognitive training. The hypothesis is that those in the spatial cognitive training group will show enhanced activation in brain regions mediating spatial processing, such as the hippocampus and parietal cortex, as well as more differentiated neural representations of imagined paths. The benefit of pinpointing the neural loci of change is the identification of potential targets for application of converging rehabilitation approaches, e.g. transcranial magnetic or electrical stimulation over parietal regions; enhancing hippocampal neurogenesis through aerobic exercise. If the present proposal is successful, subsequent research will be needed to determine how best to incorporate such training into programs that complement current O&M training.

ANALYSES

In **Specific Aim I**, each behavioral measure will be subjected to a repeated-measures ANOVA with a between-subjects factor of group (experimental, control) and a within-subjects factor of session (pre-training, post-training); the null hypothesis will be rejected in case the interaction is significant at $\alpha=0.05$. If the interaction is non-significant, the Bayes factor will be calculated to ascertain whether this (less likely) supports the null hypothesis or (more likely) reflects insufficient power (Dienes, 2014); in the latter case, the data can be used to estimate the sample size for a subsequent study. In **Specific Aim II**, the imaging measures acquired (except

for DTI) will be subjected to similar two-factor ANOVAs as in Aim I, and statistical interpretations will follow similar lines.

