We predict that spatial cognitive training, but not the control intervention, will lead to improvements in performance on the spatial imagery task, its analog in the MSL, and the various functional neuroimaging measures. There may be transfer of spatial learning to the spatial memory task, but we do not expect transfer to the verbal memory and working memory measures, indicating the spatial specificity of training. We hypothesize that spatial cognitive training, but not training on the control intervention, will lead to increases in activation in cortex along the IPS and in the FEFs as well as in the hippocampus, increased strength of connectivity between these regions in the task and resting states, and also to more differentiated representations between different paths (i.e. their representations will show higher dissimilarity). The behavioral and neuroimaging measures obtained at baseline, including DTI measures of structural connectivity between the activated brain regions, will be tested as regressors to establish whether they predict changes in the repeated measures. This will be useful to examine the impact of individual differences in pre-training spatial and verbal abilities on the effects of training, and in the design of further studies aimed at targeting interventions tuned to individual performance in specific domains.

TIMELINE

First 2 months: Set up tasks and initiate recruitment

Next 20 months: Test and train 2 subjects per month, one in each group

Last 2 months: Analyze data and prepare publications

FUTURE DIRECTIONS

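### A null group-by-session result on the verbal tests shows only that spatial training and letter-number training changed them alike; it does not by itself show that the training effect is specifically spatial.

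*Combined protocol and SAP*

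**What the plan says.** Under Study flow, both arms receive the same amount of training: "they will attend 12 training sessions of one hour each, comprising either the experimental or control intervention". Under Interventions, the comparator is described: "In the control intervention, subjects will be taught letter correspondences to the numbers (e.g. 1->A, 2->B and so on until 25->Y", with a setup and procedure similar to the experimental arm.

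Under Behavioral measures, RBANS immediate and delayed verbal memory and forward and backward Digit Span are collected before and after training, alongside the spatial measures.

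Under ANALYSES, every behavioral measure goes into a two-factor ANOVA (group, session), and "the null hypothesis will be rejected in case the interaction is significant" at 0.05. A non-significant interaction leads to a Bayes factor, meant to separate support for the null from insufficient power. The predictions paragraph then states the inference at issue: "we do not expect transfer to the verbal memory and working memory measures, indicating the spatial specificity of training".

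No section gives a within-arm criterion, an equivalence margin, an untrained arm, or an argument that letter-number learning leaves the verbal scores unchanged.

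**The concern.** The comparator suits the question whether spatial training improves spatial skill more than another activity of equal length. The specificity statement asks something different: whether spatial training leaves verbal ability unchanged. For that question the control arm must be a neutral reference on the verbal tests. Twelve hours of associating letters with numbers could plausibly exercise verbal memory, and Digit Span is itself a test with numbers, so neutrality cannot be taken for granted.

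If both activities raised verbal scores, the interaction would shrink towards zero, and the plan's wording would let a general training effect be reported as a specifically spatial one. The project is meant to inform a larger study, so that reading could be carried forward.

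**Working it through.** **What the contrast estimates.** Let r be the retest gain common to both arms, s the verbal gain caused by spatial training, and c the verbal gain caused by letter-number training.

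- Change in the spatial arm: r + s.
- Change in the control arm: r + c.
- Group-by-session interaction: (r + s) − (r + c) = s − c.

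Specificity requires s = 0. A null interaction supports s = c. The two coincide only if c = 0, and no section argues for that.

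| Case | s | c | Interaction s − c | Is training spatially specific? |
|---|---|---|---|---|
| Neither affects verbal scores | 0 | 0 | 0 | Yes |
| Both raise them equally | 0.5 | 0.5 | 0 | No |
| Both raise them equally | 0.9 | 0.9 | 0 | No |

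The planned test cannot tell these rows apart. A Bayes factor on the same contrast cannot either: support for its null is support for s = c. More participants would only estimate s − c more precisely.

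**Sample sizes for an illustration.** PARTICIPANTS says "We will recruit 60 blind participants, randomized by our CVNR statistician into two groups", which is 30 per arm if split equally, and that "this sample size has a power of 0.81 to detect an effect size of 0.9". TIMELINE says "Test and train 2 subjects per month, one in each group" for 20 months: 2 × 20 = 40, or 20 per arm. For a two-sided two-sample t test at 0.05 and an effect of 0.9 SD, power is 0.93 at 30 per arm and 0.79 at 20 per arm (0.81 by the normal approximation). The stated 0.81 thus matches 40 participants more readily than 60. That is a separate matter on which the present point does not depend, but it is why both sizes appear below.

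**Illustration with the plan's Bayes-factor step.** The documents give no prior, no cut-off and no verbal gains. I assume a Cauchy prior with scale 0.707 on the standardized difference, support for the null when the Bayes factor for the null exceeds 3, and gains in SDs of the change score. The 0.9 is borrowed from the sample-size statement, which names no outcome.

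The test statistic t is noncentral t with df = 2n − 2 and noncentrality (s − c)√(n/2). The Bayes factor exceeds 3 when |t| is below about 0.75 (n = 30 per arm) or 0.44 (n = 20).

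Probability that the Bayes factor supports the null:

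| s | n per arm | c = 0 | c = 0.2 | c = 0.3 | c = 0.5 |
|---|---|---|---|---|---|
| 0.9 | 30 | 0.3% | 2.5% | 5.7% | 20% |
| 0.9 | 20 | 0.7% | 3.4% | 6.2% | 16% |
| 0.5 | 30 | 11.5% | 31% | 43% | 55% |

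Whenever s = c, the probability is 55% at 30 per arm and 34% at 20 per arm, whatever the size of s. These are the same values as when neither arm gains.

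**Precision of what could be reported.** In SDs of change, the 95% CI half-width of one arm's change is t(0.975, n − 1)/√n: 2.045/5.477 = 0.37 at n = 30 and 2.093/4.472 = 0.47 at n = 20. For the difference between arms it is t(0.975, 2n − 2)·√(2/n): 0.52 and 0.64.

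**The case against.** **The control is never called verbal training.** This stands. The plan describes one fixed code in alphabetical order, which is neither practice of a memory test nor span practice. A reader might infer that the control demonstrably trains the tested domain; the documents do not show that. They also do not show the opposite, and the specificity claim needs it.

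**Non-significance is not automatically read as no transfer.** This also stands. A reader might count every non-significant interaction as a false claim of specificity. For s = 0.9 and 30 per arm that would give 7%, 24%, 37% and 67% for control gains of 0, 0.2, 0.3 and 0.5. The plan's Bayes-factor step does not allow that reading, and under the assumptions above the rates fall to 0.3%, 2.5%, 5.7% and 20%. The step lowers the rates but tests the same contrast, so the ambiguity stays.

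**A shared gain would not be invisible.** The ANOVA has a session factor, and a gain in both arms would appear there and in the pre/post means. That is right, but the session effect averages r + (s + c)/2, so retest gain is mixed in, and the plan states no rule for using it.

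**The prediction has a stated basis and is ancillary.** The Background reports that spatial training in sighted people did not generalize to verbal tasks, and the verbal measures are not the target of Aim I. Both are true and limit the weight of the point. Prior expectation does not change what this trial's contrast can show.

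**Conclusion.** The point holds for the verbal measures and the specificity wording only. A null interaction, or a Bayes factor favouring its null, shows that the two arms changed alike; it supports spatial specificity only on the added and undocumented assumption that letter-number training leaves verbal scores unchanged.

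The identity s − c depends on no assumed gain. The size of any bias is unknown: the documents give no control-arm verbal effect, and the percentages above are illustrations that depend on an assumed prior, cut-off and gains.

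A reader might infer that verbal transfer will be masked, or that the comparator undermines the trial's main comparisons. Neither follows. Masking is possible, not shown, and the Aim I contrasts on spatial imagery and real-world pointing ask a question that this comparator fits. This is a low-cost correction to an inference, not a flaw in the design of Aim I.

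**What to change.** In ANALYSES, for RBANS verbal memory and Digit Span:

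1. Report the pre-to-post change in each arm with its 95% CI beside the interaction. Label these changes as descriptive. They contain retest gain, so they should not replace the randomized contrast as a decision rule.
2. In the predictions paragraph, replace the specificity inference. Where the interaction is null, or the Bayes factor favours its null, conclude *no more verbal gain than after letter-number training*.

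This needs no new arm, visit or measurement. The cost is a weaker specificity claim. The within-arm intervals will also be fairly wide, about ±0.37 SD of change at 30 per arm or ±0.47 at 20.

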Imaging measures: The following imaging analyses will be conducted on data acquired before and again after training with the experimental and control interventions: (1) A univariate contrast between the experimental and control conditions will provide insight into the brain regions responsible, and the **magnitudes of activation** in key brain regions will be assessed. (2) Multivariate pattern analyses (Kriegeskorte, 2008) will be used to assess **representational similarity in the neural representations of paths**. (3) Further, we will use **multivariate effective connectivity analyses**, which our group has considerable experience with (Hampstead et al., 2011; [name] et al., 2013; Lacey et al., 2014), to examine patterns of connectivity during task performance. (4) In addition, we will assess **resting-state connectivity** patterns using the activated regions as seeds. (5) Finally, we will also acquire diffusion tensor imaging (DTI) scans to assess **structural connectivity**.

Imaging design: The same spatial imagery task as outlined above will be used during fMRI scanning in an event-related design, with pseudorandomly interleaved trials of a control task requiring judgment of whether the majority of numbers in the audio sequence are odd or not. On each trial, the stimulus presentation will occupy 4s or 5s, depending on whether the sequence comprises 4 or 5 steps in the grid. These two trial durations will be interleaved in pseudorandom order, as will experimental and control trials. Participants will be verbally instructed to make their keypress response following the last auditory cue. A blank interval varying from 4-8s will intervene between trials: this jitter allows for better estimation of the signal on each trial than designs with a fixed inter-trial interval. Each run of trials will also include six pseudorandomly interspersed 10s blank periods for estimation of baseline signal. Functional runs will last 9min 20s, comprising a total of 40 trials (20 experimental and 20 control). 4 such runs will be conducted.

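### Every baseline measure is tested as a predictor of change in every repeated measure, with no multiplicity control, validation or exploratory label, so chance predictors are expected and cannot by themselves guide targeting

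*Combined protocol and SAP*

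**What the plan says.** The second paragraph of ANALYSES states that the behavioural and neuroimaging measures taken at baseline, DTI included, "will be tested as regressors to establish whether they predict changes in the repeated measures". It gives the use of the results as examining individual differences in the effects of training, and as helping "in the design of further studies aimed at targeting interventions tuned to individual performance in specific domains".

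The candidate measures are listed under PROCEDURES. Behavioral measures covers the imagery task, the walking task and the neuropsychological tests. Imaging measures covers activation, representational similarity, effective connectivity and resting-state connectivity, and ends with the statement that "we will also acquire diffusion tensor imaging (DTI) scans to assess" structural connectivity.

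The first paragraph of ANALYSES sets the rule for the main tests: "the null hypothesis will be rejected in case the interaction is significant at" 0.05, measure by measure, with DTI left out of the repeated-measures analyses. For the predictor analysis nothing comparable is given. It does not say whether regressors enter singly or jointly, whether the arms are pooled, whether a baseline-by-group term is fitted, which outcome matters most, how multiplicity is handled, or how prediction is validated.

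The only sample-size statement, under PARTICIPANTS, is that "this sample size has a power of 0.81 to detect an effect size of 0.9". That concerns a single effect and not prediction.

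**The concern.** Crossing many candidate predictors with many outcomes at 0.05 each, in a few dozen people, produces significant pairs when nothing is predictive. The pairs that survive are the most extreme of the set, so their correlations look substantial. The plan has no step that would tell such results from real ones, and its verb, *establish*, invites readers to take them as settled.

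A second problem does not depend on the number of tests. Correlating a baseline score with the change computed from that same score gives a negative association even if training works equally well for everyone. The plan wants to know who benefits from training. That is a question about a baseline-by-group interaction, which is not specified.

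At stake is the next study. This project is meant to inform a larger trial, and false predictors could shape its eligibility, stratification or tailoring.

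**Working it through.** **Inputs**
- Sample size (PARTICIPANTS): "We will recruit 60 blind participants, randomized by our CVNR statistician into two groups", so 30 per arm if allocation is equal.
- TIMELINE: "Test and train 2 subjects per month, one in each group" for 20 months, so 2 × 20 = 40, or 20 per arm.
- Predictors: eight behavioural scores (imagery accuracy, imagery response time, pointing error, haptic Corsi, RBANS immediate and delayed memory, digit span forward and backward) plus five imaging families. One summary per imaging family is my assumption, and a low one. Total 8 + 5 = 13.
- Outcomes: the same eight scores plus four imaging families, since DTI is not analysed as a repeated measure. Total 8 + 4 = 12.

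**The plan's own figure.** For d = 0.9 and two-sided 0.05, power ≈ Φ(0.9 × √(n/2) − 1.96). With n = 30 per arm this is 0.94 (exact t: 0.93). With n = 20 it is 0.81 (exact t: 0.79). The stated 0.81 therefore fits 40 participants and not 60. That is a separate inconsistency to reconcile. Here it means that the prediction sample could be 60 or 40.

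**Number of tests, regressors taken one at a time.** Expected false positives = 0.05 × tests; P(at least one) = 1 − 0.95^tests if independent.

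| Set | Tests | Expected | P(≥1), independent |
|---|---|---|---|
| 13 × 12 | 156 | 7.8 | 0.9997 |
| Behavioural only, 8 × 8 | 64 | 3.2 | 0.96 |
| One outcome, 13 × 1 | 13 | 0.65 | 0.49 |

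Measures will be correlated, so I also simulated the null with a common correlation of 0, 0.3 or 0.5 within predictors and within outcomes. The expected count stays near 7.8. P(at least one) falls only to about 0.95 at correlation 0.5. For one outcome it falls to about 0.34. The median largest |r| over the 156 pairs is 0.47 to 0.50 at n = 30 and 0.34 to 0.36 at n = 60; the thresholds for p < 0.05 are 0.36 and 0.25.

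**Joint model, if one were used.** Expected null in-sample R² = k/(n − 1).
- n = 30: 13/29 = 0.45
- n = 60: 13/59 = 0.22
- n = 20: 13/19 = 0.68
- n = 40: 13/39 = 0.33

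The median leave-one-out R² on the same kind of noise is about −1.1 at n = 30 and −0.34 at n = 60, so the apparent fit does not carry over to new people.

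**Baseline against its own change.** With equal variances and pre-post correlation ρ, corr(baseline, change) = −√((1 − ρ)/2).
- ρ = 0.5: −0.50
- ρ = 0.7: −0.39
- ρ = 0.8: −0.32

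All three exceed the n = 60 threshold of 0.25 in size. Twelve of the 156 pairs set a measure against its own change, so the 7.8 understates the number of misleading hits.

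**The case against.** The strongest reply is that this is a secondary analysis in a project that the opening Relevance paragraph calls a proof of concept. The results are to inform the design of further studies, and no targeting rule is planned from this trial. That stands: a hypothesis-generating role is legitimate. It supports adding the label, not leaving it out.

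The search is also not wholly open. DTI and the resting-state seeds are tied to activated regions, and the hypotheses name the IPS, the FEFs and the hippocampus. This narrows the anatomy but caps neither predictors nor outcomes.

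Several stronger readings are tempting and are not supported:
- A reader might count three regions or region pairs per imaging family, reach 8 + 15 = 23 predictors, and quote a null R² of 23/29 = 0.79 in the trained arm. The documents specify neither a joint model, nor an analysis of the trained arm alone, nor three summaries per family. The regions are named in hypotheses about training-induced change.
- A reader might infer that a high null R² means a high false-positive rate. It does not. The F test allows for the number of regressors, and in null simulations it rejected in about 5% of runs. The false positives come from the number of tests.
- A reader might infer that a spurious predictor is near certain for any one outcome. With 13 predictors it is 0.34 to 0.49.
- A reader might infer that the Aim I and Aim II group-by-session tests are compromised. This point does not touch them.

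**Conclusion.** The concern holds. Followed as written, the predictor analysis is expected to yield about eight nominally significant predictor-outcome pairs from noise. At least one is close to certain (about 0.95 to 1.00), and the largest would look persuasive. Own-baseline coupling adds further associations that say nothing about who benefits from training. The results cannot by themselves guide the targeting of later interventions; they can suggest hypotheses.

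The size rests on three assumptions: one summary per imaging family, regressors tested singly at 0.05, and within-set correlations of up to 0.5. More imaging summaries would raise the count. The behavioural scores alone still give 3.2 expected false positives. The joint-model R² values apply only if a joint model is fitted. The coupling figures assume equal pre and post variances. The conclusion is the same whether 60 or 40 people are enrolled.

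**What to change.** Change the ANALYSES text as follows.

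1. Label the analysis hypothesis-generating, and say that it will *explore whether baseline measures may predict* change rather than *establish* it.
2. Name one outcome and a short list of predictors in advance. The length of the list is a matter of judgement.
3. Use both arms. Model the post-training score adjusted for its own baseline, and test predictors of training benefit through the baseline-by-group term, not through correlation with change.
4. For all remaining predictors, report cross-validated performance with a permutation p-value that repeats the whole selection across predictors and outcomes. The choice of penalised method is open.

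Item 3 is needed alongside item 4. Cross-validation and permutation alone would pass the own-baseline association as genuine prediction of change.

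As an illustration, one outcome with two predictors and Holm adjustment cuts 156 tests to 2 and holds the family-wise error at 0.05 or less (1 − 0.95² = 0.0975 if unadjusted).

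The cost is SAP wording, modest analysis code and fewer nominal findings; no new data are needed. Power stays low. At 0.025 and 80% power, the smallest detectable correlation is tanh((2.24 + 0.84)/√(n − 3)), which is 0.53 in one arm of 30 and 0.39 in 60 pooled. A between-arm difference needs about 0.69 against 0, from tanh(3.08 × √(2/27)). The SAP should say so, so that a null result is not read as absence of moderation.
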